8.3.7.2 Statistical analysis of e-diary scores

The derived e-diary NRS score will be analysed using the same statistical analysis as for the Imorphics MRI described in detail in section 8.1.1. Outputs from these statistical analysis will be similar to that as presented for the MRI data (see example figures and table section 8.1.1.) however outputs and analysis of the e-diary scores will be based on the visits when the e-diary assessments were recorded.

8.3.8 Biomarkers from Serum and Urine Samples

The observed values and the change from baseline values for the serum CTX-I and urinary CTX-II biomarkers will be listed and summarized descriptively. Note the baseline visit is defined as visit 2 in study MIV-711-202 for study Group B.

Time-Integrated-Concentrations (TIC) will be derived for each serum CTX-I and urinary CTX-II biomarkers. For each biomarker the mean TIC value and the standard deviation (SD) of the TIC regarding the time period on drug will be derived. Thus, for group A the time period will include 26 + 26 weeks whereas the time period for group B will be the 26 weeks in study MIV-711-202. For each biomarker a Z-score will be derived by subtracting the mean and dividing by SD. TIC results and associated Z-scores will be listed and summarized for each subject.

Box plots will be used to visualize the distribution of TIC response and biomarker Z-score.

PAREXEL International Statistical Analysis Plan

Medivir
Protocol: MIV-711-202

Final 1.0
16 January 2018

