8.3.8.1 Statistical analysis biomarkers from serum and urine samples

The statistical analysis of the serum CTX-I and urinary CTX-II biomarkers will be performed using the same statistical analysis as for the Imorphics MRI described in section 8.1.1. Outputs from these statistical analysis will be similar to that as presented for the MRI data (see example figures and table section 8.1.1.) however outputs and analysis of the biomarker scores will be based on the visits when the biomarker assessments were recorded.

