Figure 14.2.3.2	Estimated change from visit 2 MIV-711-201 \pm 95% CI for NRS Items by Week and Group, ITT Population
Figure 14.2.4.1	Estimated Mean \pm 95% CI for WOMAC Items by Week and Group, ITT Population
Figure 14.2.4.2	Estimated change from visit 2 MIV-711-201 \pm 95% CI for WOMAC Items by Week and Group, ITT Population
Figure 14.2.4.3	Estimated Mean \pm 95% CI for Normalized WOMAC Scores by Week and Group, ITT Population
Figure 14.2.4.4	Estimated change from visit 2 MIV-711-201 \pm 95% CI for Normalized WOMAC Scores by Week and Group, ITT Population
Figure 14.2.5.1	Estimated Mean \pm 95% CI for NRS E-Diary by Week and Group, ITT Population
Figure 14.2.5.2	Estimated change from visit 2 MIV-711-201 \pm 95% CI for NRS e-diary by Week and Group, ITT Population
Figure 14.2.5.3	Estimated Mean \pm 95% CI for Percentage Score E-Diary Analgesic Usage by Week and Group, ITT Population
Figure 14.2.5.4	Estimated change from visit 2 MIV-711-201 \pm 95% CI for Percentage Scores of E-Diary Analgesic Usage by Week and Group, ITT Population
Figure 14.2.6.1	Estimated Mean \pm 95% CI for Efficacy Biomarkers by Week and Group, ITT Population
Figure 14.2.6.2	Box Plots of Time Integrated Concentrations and their Z-Scores for Efficacy Biomarkers from Serum and Urine Samples by Group, ITT Population

PAREXEL International Statistical Analysis Plan

Medivir
Protocol: MIV-711-202

Final 1.0
16 January 2018

Figure 14.2.7.1	Mean \pm 95% CI Profiles of Observed Systolic Blood Pressure by Week and Group, SAF Population
Figure 14.2.7.2	Mean \pm 95% CI Profiles of Observed Heart Rate by Week and Group, SAF Population
Figure 14.2.8.1	Mean (95% CI) Profiles of Observed QTcB Interval by Week and Group, SAF Population
Figure 14.2.8.2	Mean (95% CI) Profiles of Observed QTcF Interval by Week and Group, SAF Population

PAREXEL International Statistical Analysis Plan

Medivir
Protocol: MIV-711-202

Final 1.0
16 January 2018

13. Listings

TLF Number	Title
Listing 16.2.1.1	Patient Disposition
Listing 16.2.1.2	Patients Excluded from Analysis Populations
Listing 16.2.1.3	Enrolled Patients Who Did Not Meet All Eligibility Criteria
Listing 16.2.1.4	Exclusion Tests
Listing 16.2.2.1	Protocol Deviations
Listing 16.2.4.1	Demographics
Listing 16.2.4.2	Medical History
Listing 16.2.5.1	Prior and Concomitant Medications
Listing 16.2.5.2	Dose Administration at Clinic Visits
Listing 16.2.5.3	Dose Administration Compliance, ITT Population

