	MIV-711-201	SD	xx.xx	xx.xx	xx.xx	xx.xx
	WEEK 4	Median	xx.x	xx.x	xx.x	xx.x
		Min	xx	xx	xx	xx
		Max	xx	xx	xx	xx
		n	nn	nn	nn	nn
	VISIT 6	Mean	xx.x	xx.x	xx.x	xx.x
	MIV-711-201	SD	xx.xx	xx.xx	xx.xx	xx.xx
	WEEK 14	Median	xx.x	xx.x	xx.x	xx.x
		Min	xx	xx	xx	xx
		Max	xx	xx	xx	xx

Etc....

Baseline is defined as: Visit 2 in the MIV-711-201 for Group, Visit 2 in the MIV-711-202 for Group B

Programming note: table will include parameters Serum CTX-I and urine CIX-II

PAREXEL International SAP Amendment Shells

Medivir
Protocol: MIV-711-202

Final 1.0
16 January 2018

Medivir
Protocol Number: MIV-711-202

Page X of Y

Table 14.2.7.1
Efficacy Biomarkers from Serum and Urine Samples - Summary of Observed and Change from Baseline Values
ITT Population

Parameter = Serum CTX-I

AM/PM	Visit	Statistic	Group A N = x		Group B N = x	
			Observed N = x	Change N = x	Observed N = x	Change N = x
		n	nn	nn	nn	nn
AM Response	VISIT 8	Mean	xx.x	xx.x	xx.x	xx.x
	MIV-711-201	SD	xx.xx	xx.xx	xx.xx	xx.xx
		Median	xx.x	xx.x	xx.x	xx.x
	WEEK 26	Min	xx	xx	xx	xx
		Max	xx	xx	xx	xx
		n	nn	nn	nn	nn
	VISIT 2	Mean	xx.x	xx.x	xx.x	xx.x
	MIV-711-202	SD	xx.xx	xx.xx	xx.xx	xx.xx
		Median	xx.x	xx.x	xx.x	xx.x
	WEEK 27	Min	xx	xx	xx	xx
		Max	xx	xx	xx	xx
		n	nn	nn	nn	nn
	VISIT 4	Mean	xx.x	xx.x	xx.x	xx.x
	MIV-711-202	SD	xx.xx	xx.xx	xx.xx	xx.xx
		Median	xx.x	xx.x	xx.x	xx.x
	WEEK 40	Min	xx	xx	xx	xx
		Max	xx	xx	xx	xx
		n	nn	nn	nn	Nn
	VISIT 5	Mean	xx.x	xx.x	xx.x	xx.x
	MIV-711-202	SD	xx.xx	xx.xx	xx.xx	xx.xx
		Median	xx.x	xx.x	xx.x	xx.x
	WEEK 52	Min	xx	xx	xx	xx
		Max	xx	xx	xx	xx

Baseline is defined as: Visit 2 in the MIV-711-201 for Group A, Visit 2 in the MIV-711-202 for Group B

Programming note: table will include parameters Serum CTX-I and urine CIX-II

PAREXEL International SAP Amendment Shells

Medivir
Protocol: MIV-711-202

Final 1.0
16 January 2018

Medivir
Protocol Number: MIV-711-202

Page X of Y

Table 14.2.7.2
Time-Integrated Concentrations (TIC) and Their Z-scores for Efficacy Biomarkers from Serum and Urine Samples
Summary of Observed Values
ITT Population

Parameter = TIC Serum CTX-I

Statistic	Group A N = x	Group B N = x
n	nn	nn
Mean	xx.x	xx.x
SD	xx.xx	xx.xx
Median	xx.x	xx.x
Min	xx	xx
Max	xx	xx

Programming note: table will include parameters TIC Serum CTX-I, TIC urine CIX-II, Z-Score Serum CTX-I, Z-Score urine CIX-II

PAREXEL International SAP Amendment Shells

Medivir
Protocol: MIV-711-202

Final 1.0
16 January 2018

Medivir
Protocol Number: MIV-711-202

Page X of Y

Table 14.2.7.3

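### The CTX-I and CTX-II Z-scores are standardised by the mean and SD of the same on-drug TICs, so they carry no information on a drug effect

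*SAP*

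**What the plan says.** SAP 8.3.8 covers serum CTX-I and urinary CTX-II. "For each biomarker the mean TIC value and the standard deviation (SD) of the TIC regarding the time period on drug will be derived", and then "For each biomarker a Z-score will be derived by subtracting the mean and dividing by SD". The windows differ: "for group A the time period will include 26 + 26 weeks whereas the time period for group B will be the 26 weeks" of the extension study. The section brings in no baseline, placebo-period or external reference for the Z-score. It does not say whether the mean and SD are taken per group or over both groups, and it gives no formula for TIC.

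Three outputs carry these quantities:

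- Table 14.2.7.2 has n, mean, SD, median, minimum and maximum by group. Its programming note reads "table will include parameters TIC Serum CTX-I, TIC urine CIX-II, Z-Score Serum CTX-I, Z-Score urine CIX-II".
- Figure 14.2.6.2 is titled "Box Plots of Time Integrated Concentrations and their Z-Scores for Efficacy Biomarkers from Serum and Urine Samples by Group, ITT Population".
- Listing 16.2.6.24 shows each patient's TIC and Z-score, with TIC in ug/L for CTX-I and ng/mmol for creatinine-corrected CTX-II.

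None of the three has a pre-drug column.

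The same part of the SAP plans two other biomarker analyses. For Table 14.2.7.1, "The observed values and the change from baseline values for the serum CTX-I and urinary CTX-II biomarkers will be listed and summarized descriptively". For Table 14.2.7.3, "The statistical analysis of the serum CTX-I and urinary CTX-II biomarkers will be performed using the same statistical analysis as for the Imorphics MRI". Protocol 9.1.3 rules out comparisons between Study Populations A and B.

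**The concern.** The exploratory objective (Protocol 3.4, SAP 2.4) is the effect of MIV-711 on these markers, and the TIC outputs are titled as efficacy biomarkers. A reader who meets a group Z-score under that title will tend to take it as evidence about effect. Standardising a set of values by its own mean and SD removes its location and scale, and that is where a reduction on drug would appear. The Z rows would look the same whether the drug did nothing or removed most of the marker. Because the TIC formula and the reference set are both left open, two programmers could also follow the text and produce different tables.

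**Working it through.** The SAP states no figure for this output, so there is nothing to reproduce. The core result is algebra; the simulation only illustrates it.

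**Inputs from the documents.** On-drug TICs, their own mean and SD, and windows of 52 and 26 weeks (SAP 8.3.8); 50 to 80 patients in total (Protocol 5.4).

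**Assumptions.** The documents give no between-patient CV and no A/B split. I used lognormal pre-drug levels with CV 0.3 and 0.6, splits of 40/10 and 60/20, a between-patient SD of 0.10 in the reduction, and 400 runs per setting. Mean reductions were 0, 20, 45 and 72%. Protocol 2.2 quotes 55 and 72%, but its wording leaves unclear whether these are reductions or remaining levels, so the grid is illustrative.

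**Step 1: algebra.** Z_i = (T_i − T̄)/s. The deviations T_i − T̄ sum to zero, so mean Z = 0. The SD of Z is s/s = 1. If the drug multiplies every TIC by c = 1 − r, then T̄ becomes cT̄ and s becomes cs, so every Z_i is unchanged. Numerically, multiplying a set of TICs by 0.80, 0.55 or 0.28 changed no Z by more than 2 × 10⁻¹⁵, which is rounding error.

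**Step 2: simulation.** Column two uses per-group scaling as in SAP 8.3.8. Column four replaces the reference by the pre-drug mean and SD.

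| Reduction | Z mean, SD (each group) | Group A raw TIC mean (pre-drug about 1) | Group A mean Z, pre-drug reference (CV 0.6 to 0.3) |
|---|---|---|---|
| 0% | 0.00, 1.00 | about 1.00 | about 0 |
| 20% | 0.00, 1.00 | 0.80 | −0.35 to −0.62 |
| 45% | 0.00, 1.00 | 0.55 | −0.76 to −1.39 |
| 72% | 0.00, 1.00 | 0.28 | −1.22 to −2.21 |

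Column four follows roughly −r/CV. For example, −0.20/0.3 = −0.67, slightly larger than the simulated −0.62 because the simulated pre-drug value carries visit-to-visit error that widens its SD.

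**Step 3: pooled scaling.** The overall mean and SD are again 0 and 1. With a common effect and time-averaged TIC, the A minus B difference in mean Z was −0.03 to 0.06 at every effect size. The only contrast left is A against B, with both groups on drug, and the protocol excludes that comparison.

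**Step 4: pooled scaling with TIC as an un-normalised area.** With identical concentrations averaging 1 in both groups, the mean areas are 52 and 26, a gap of 26. For CV 0.3 and a 40/10 split, the pooled variance is about [39 × (0.3 × 52)² + 9 × (0.3 × 26)² + (40 × 10/50) × 26²]/49 = (9491 + 548 + 5408)/49 = 315. The SD is 17.8 and the gap is 26/17.8 = 1.46 SD. The simulation, which adds a little measurement error, gives 1.42. Over both CVs and both splits, with no drug effect, the range is 0.85 to 1.42 SD.

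**The case against.** The strongest reply is that the SAP never says the Z-score is meant to estimate a drug effect. Section 8.3.8 has TIC and Z listed and summarised for each subject, with box plots to show their distribution. That fits a relative-position descriptor which puts two markers with different units on one scale, and self-standardisation is ordinary for that use. This stands for the patient-level listing. It does not justify printing a group mean and SD of Z, which are known before any data arrive under per-group scaling; the median, minimum and maximum then show only the shape of the distribution.

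A reader might infer that Table 14.2.7.2 and Figure 14.2.6.2 as a whole cannot show a drug effect, or that the biomarker objective goes unmet. The documents support neither. Both outputs also carry raw TIC, which moves with the drug; its weakness is the missing pre-drug comparator and formula. Table 14.2.7.1 gives change from a pre-drug baseline by visit, and Table 14.2.7.3 models the visits across both studies.

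A reader might also infer that the unequal windows will drive the groups apart. That needs both pooled scaling, which is not stated, and an un-normalised area. The concentration units in Listing 16.2.6.24 point to time-averaging, under which this artefact disappears. A listing header is still not a derivation rule, so the ambiguity should be closed.

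Finally, side-by-side group columns appear throughout the SAP, and no A-minus-B difference in TIC or Z is planned.

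**Conclusion.** The point holds for the Z-scores. Their mean and SD are fixed at 0 and 1, per group or overall, and a common proportional effect cancels exactly. This rests only on the wording of SAP 8.3.8, not on the assumed CVs, group sizes or reductions. If reductions vary between patients, individual Z values can shift relative to one another, but the mean and SD remain fixed.

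Two smaller defects go with it: raw TIC lacks a pre-drug comparator in its own table and figure, and TIC has no stated formula. The 0.85 to 1.42 SD separation is conditional on the less likely reading and on assumed CVs and splits.

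Severity is minor. This is one exploratory descriptive output in a study not powered for confirmatory analysis, and other tables address the biomarker effect.

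**What to change.** In SAP 8.3.8:

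1. Define TIC as the area under the concentration curve divided by on-drug duration, and name the visits that enter the area.
2. Summarise and plot TIC by group as percentage change from each patient's own pre-drug baseline: Visit 2 of MIV-711-201 for Group A and Visit 2 of MIV-711-202 for Group B.
3. Drop the Z-score rows from Table 14.2.7.2 and the Z panels from Figure 14.2.6.2, or standardise Z by the mean and SD of those same pre-drug baseline values. If the second option is chosen, state which patients supply the mean and SD, and note that the SD of a single-visit value differs from that of a multi-visit average. Patient-level self-standardised Z may stay in Listing 16.2.6.24, labelled as relative position.
4. Reconcile the Group B biomarker baseline. SAP 8 and 8.3.8 give Visit 2 of MIV-711-202, while the footnote to Listing 16.2.6.23 gives Visit 8 of MIV-711-201.

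The cost is SAP wording and one extra derivation, plus loss of the self-standardised scale in the summary. Both study schedules already include the pre-drug samples.

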8.3.8.1 Statistical analysis biomarkers from serum and urine samples

The statistical analysis of the serum CTX-I and urinary CTX-II biomarkers will be performed using the same statistical analysis as for the Imorphics MRI described in section 8.1.1. Outputs from these statistical analysis will be similar to that as presented for the MRI data (see example figures and table section 8.1.1.) however outputs and analysis of the biomarker scores will be based on the visits when the biomarker assessments were recorded.

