Cathepsin K is a cysteine protease predominantly expressed in the osteoclast and intimately involved in bone resorption. It is also expressed in chondrocytes and synovial fibroblasts. Under normal physiological conditions, cathepsin K degrades key bone matrix proteins such as type I collagen. Cathepsin K is also expressed in chondrocytes in cartilage where it is able to cleave collagen type II and aggrecan, the main components of the cartilage matrix, leading to cartilage destruction. Consistent with these observations, transgenic mice that over-express cathepsin K spontaneously develop synovitis and cartilage degeneration.[26] Some fragments resulting from cathepsin K cleavage serve as biomarkers for its activity both *in vitro* and *in vivo* as further described below.

Cleavage of type I collagen results in release of the C-terminal telopeptide of collagen type I (CTX-I), a biomarker that has been used extensively as a surrogate measure of bone resorption.[27] Cartilage degradation can be assessed by measuring the C-terminal telopeptide of collagen type II (CTX-II), which is a fragment released during cartilage degeneration in OA. In OA patients, increased CTX-II levels are associated with loss of cartilage integrity and are linked to disease burden, progression and radiographic scoring.[12, 28, 29] Bone-acting agents do not solely affect CTX-I but also CTX-II, most likely indirectly due to their anti-resorptive effects on subchondral bone. Reductions in CTX-II levels of 20-40% by anti-resorptive drugs are associated with attained pain and structural primary endpoints in OA patient studies.[14, 16, 30, 31] To summarise the relevance of these two biomarkers, the

reduction of CTX-I and CTX-II in blood and urine are used as indicators of reduced bone resorption and cartilage degradation, respectively, which are believed to translate into beneficial effects counteracting joint degeneration in OA.

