#### 9.5.2.4 Statistical Methodology for Secondary Endpoints

For Study Population B, the safety and tolerability of 200 mg MIV-711 for 26 weeks will be studied in OA patients with clinical worsening during the placebo treatment in the MIV-711-201 study. Safety and tolerability will be assessed descriptively in summary tables presented over time.

All other secondary analyses will be undertaken using Study Population A, while they will be undertaken as exploratory analyses on Study Population B.

For Study Population A all secondary outcome variables will be analysed using descriptive summary tables presenting statistics for, number of non-missing values means, medians, standard deviations, minimum and maximum values. Frequency tables (counts and

percentages) will be presented in tables where appropriate. Figures of secondary response over time will be presented as appropriate.

For all outcome variables analysed using a linear model, distributional assumptions will be checked using examination of empirical distributions and model residuals. If necessary, data will be transformed prior to analysis if this improves the model fit, or normalises the distribution of the residuals. Non-parametric methods may be applied if appropriate.

For the analysis of secondary endpoints, alternate statistical methods maybe considered that will include the use of generalised linear models that account for the response variable having a “non-normal” distribution. Additional details will be provided in the SAP.

All secondary outcomes will be summarised descriptively (mean, SD, median, minimum and maximum for continuous data and counts and percentages for categorical data).

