7.9 Dose Administration

Information collected per the dose administration CRF will be listed including patient number, visit, date and time of administration, number of capsules dispensed and number of capsules returned.

The number and percentage of patients who received IMP will be summarized for each on site visit. Descriptive statistics will be used to summarize drug accountability as the number of capsules returned for each on site study visit by treatment.

Compliance will be derived as the number of days patient were exposed to IMP. 100% compliance will be considered for dosing during the period Visit 2 to Visit 5. The number of capsules used will be derived as the number of capsules dispensed minus the number of capsules returned. Subjects with less than 100% compliance will be identified among those who have results for “Reason not all unused Capsules returned”. The compliance will not be calculated for withdrawn patients, as the date of the last IMP dose taken is not captured in the database.

8. Pharmacodynamic Analysis – Efficacy

The baseline will be the last valid assessment prior to first dose of 200 mg MIV-711, i.e. the baseline visit is defined as

- Visit 2 in study MIV-711-201 for study group A
- Visit 8 in study MIV-711-201 for study group B

The exception is for the biomarkers in study group B, where the baseline visit is defined as visit 2 in the present study (MIV-711-202).

The change from baseline for visit X will be calculated as the (visit X – baseline visit) difference in observed values. Note that the change from baseline will be calculated for all visits in study MIV-711-201 and study MIV-711-202 where the actual endpoint has

PAREXEL International Statistical Analysis Plan

Medivir
Protocol: MIV-711-202

Final 1.0
16 January 2018

been observed, i.e. not only for visits in study MIV-711-202 succeeding the baseline visit.

All efficacy analyses will be made on the ITT population if not stated otherwise.

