8.1 Imorphics MRI Assessments

The analyses of the imorphics MRI will be made on the ITT group and on the PPS population.

The observed values and the derived change from baseline values will be listed and summarized descriptively for the following MRI variables:

- MRI of the bone area of the medial femur for the target knee.
- MRI of the cartilage thickness for the target knee.
 - CM_FEMUR_THCTAB: Average thickness of cartilage in the central medial femur region
 - CM_TIBIA_THCTAB: Average thickness of cartilage in the central medial tibia region
- MRI of the total bone marrow lesion volume for the target knee

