8.1.1 Statistical Analysis – Imorphics MRI Assessments

A linear mixed effects model will be used to assess the behaviour of the MRI response over the entire period of the two studies, i.e. from visit 2 in study MIV-711-201 to visit 5 in study MIV-711-202. The model will include fixed factors for study group (A or B), visit, group*visit interaction, baseline analgesic user (Yes/No), and random effect for site and patient.

Patients considered analgesic users at baseline will be identified via concomitant medication analgesic usage. A patient exposed to a prescribed analgesic and ongoing medication at time of the first 200 mg MIV-711 intake (visit 2 study MIV-711-201 for patients in group A and visit 2 study MIV-711-202 for group B) will be considered as a baseline analgesic user.

The dependent variable in the linear mixed model is the observed MRI score. Separate mixed model analyses will be considered for each of the MRI endpoints noted in section 8.1. The following SAS code will be used as default, but a reduced model may be used in case of convergence issues:

```
PROC MIXED data=;  
  CLASS patient visit group baseline_conmed_pain_use;
```

PAREXEL International Statistical Analysis Plan

Medivir
Protocol: MIV-711-202

Final 1.0
16 January 2018

```
MODEL MRI_score = group visit group*visit baseline_conmed_pain_use/ DDFM=KR ;  
RANDOM site;  
REPEATED visit / SUBJECT=patient TYPE=UN;  
LSMEAN group*visit / diff CL ALPHA=0.1 ;  
RUN;
```

In case of convergence issues, a reduced model will be used to achieve convergence. The first two model reductions that will be considered are the following:

1. Simplify the covariance structure by using a compound symmetry covariance structure instead of unstructured.
2. Omit the random effect of site

The mean level and the change from visit 2 in study MIV-711-201 will be estimated for each population*visit combination in the model above together with the corresponding 90% confidence interval. The estimates and confidence intervals will be tabulated and visualized over visits with the two groups in the same table/figure (see example figures and example table below). In this example table and example figures (Figure 1, Figure 2 and Table 1), 'Population A' and 'Population B' refer to Group A and Group B.

PAREXEL International Statistical Analysis Plan

Medivir
Protocol: MIV-711-202

Final 1.0
16 January 2018

Figure 1 Example figure of estimated mean levels

[figure not shown]
[figure not shown]

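### CTX-I and CTX-II are modelled on the raw scale, so the percentage change the protocol speaks of gets no confidence interval, and the protocol's residual check is not carried into the SAP

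*SAP*

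**What the plan says.** SAP 8.3.8.1 sends both biomarkers to the model of section 8.1.1: "The statistical analysis of the serum CTX-I and urinary CTX-II biomarkers will be performed using the same statistical analysis as for the Imorphics MRI". In 8.1.1, "The dependent variable in the linear mixed model is the observed MRI score", and the covariance statement is "REPEATED visit / SUBJECT=patient TYPE=UN". The only stated departure from the model is for fitting failure: "In case of convergence issues, a reduced model will be used to achieve convergence".

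The scale of change is set at the start of SAP section 8: "The change from baseline for visit X will be calculated as the (visit X – baseline visit) difference in observed values". The biomarker model shell (Table 14.2.7.3) follows this, with LS means per group and visit, differences from Visit 2 of MIV-711-201, and no ratio or percentage. Table 14.2.7.1 and Listing 16.2.6.23 likewise give observed values and absolute change.

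The protocol speaks of these markers in percentages. Section 2.1 says of other drugs: "Reductions in CTX-II levels of 20-40% by anti-resorptive drugs are associated with attained pain and structural primary endpoints". Section 2.2 expresses the Phase I effects of MIV-711 on serum CTX-I and urinary CTX-II as percentages relative to baseline.

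Protocol 9.5.2.4 says that distributional assumptions will be checked for all outcome variables analysed with a linear model and, where necessary, that "data will be transformed prior to analysis if this improves the model fit". It allows non-parametric and generalised linear alternatives and leaves details to the SAP. Total BML volume, listed in SAP 8.1 as "MRI of the total bone marrow lesion volume for the target knee", goes through the same model and is a secondary endpoint in Population A.

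**The concern.** The planned biomarker output does not directly estimate the quantity the protocol uses to interpret the markers. A reader who wants to know whether CTX-II fell by something like 20-40% will find absolute differences with intervals, but no interval for the percentage.

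If each patient's marker falls by roughly the same fraction, the absolute fall is largest in patients with high baselines. The mean change and its standard error are then driven by those patients, and the estimate is noisier than on the log scale.

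The protocol has a safeguard that could reveal this, namely a look at distributions and residuals with room to transform. The SAP adds a mixed model with intervals for biomarkers that protocol 9.5.3.2 planned to describe only or report separately, and it does not bring the safeguard along. A scale chosen after the data are seen would be post hoc.

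**Working it through.** The plan gives no sample size, SD, CV or target difference for these endpoints, so there is no figure to reproduce. The check has a textual part and an illustrative part.

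**Text side by side**

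- Response: observed value (SAP 8.1.1, applied by 8.3.8.1).
- Change: arithmetic difference (SAP section 8, Table 14.2.7.3).
- Fallback: non-convergence only (SAP 8.1.1).
- Box plots: for the time-integrated concentrations (TIC) and Z-scores (SAP 8.3.8). They do not check the mixed model.
- Percentage change: defined for the OARSI-OMERACT response (SAP 8.3.4) but not for the biomarkers.
- Protocol 9.5.2.4: check for all outcomes analysed with a linear model; transformation conditional.

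**What can be recovered from the planned table**

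For Group A, percentage change in means = LS mean difference ÷ LS mean at Visit 2 of MIV-711-201. For Group B the reference is the LS mean at Visit 2 of MIV-711-202, which is also tabulated. So the point percentage is available. Its interval is not, because it depends on two estimated means and their covariance, which the table does not show.

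**Size if the response is multiplicative (assumed)**

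Assume a lognormal marker, follow-up = q × baseline level, between-patient CV b = 0.5 to 0.8, within-patient CV w = 0.3, and q = 0.8 or 0.6 (20% or 40% reduction). Per-patient squared signal-to-noise for a paired change:

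- Raw: (1−q)² / V, with V = (1+b²)[(1+q²)(1+w²) − 2q] − (1−q)², in units of the squared baseline mean.
- Log: (ln q)² / [2 ln(1+w²)], with 2 ln 1.09 = 0.1724.

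Low corner, b = 0.5, q = 0.8: V = 1.25 × (1.64 × 1.09 − 1.6) − 0.04 = 0.1945. Raw = 0.04/0.1945 = 0.206. Log = 0.0498/0.1724 = 0.289. Ratio 1.40.

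High corner, b = 0.8, q = 0.6: V = 1.64 × (1.36 × 1.09 − 1.2) − 0.16 = 0.3031. Raw = 0.16/0.3031 = 0.528. Log = 0.2609/0.1724 = 1.514. Ratio 2.87.

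These are large-sample ratios. With 20,000 simulated data sets at n = 15 and n = 40, the ratio of squared median t (log over raw) ran from 1.23 to 2.39. It is smaller because, in small skewed samples, the raw-scale SD usually falls short of its population value, which flatters the raw t.

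**How much this changes in practice**

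In the same scenarios, the ratio of raw means recovered the true 20% and 40% reductions (median), with an SD of 4 to 11 percentage points against 4 to 9 for the log estimate. In the 2.39 scenario (n = 40, b = 0.8, 40% reduction) the interval excluded zero in 99.9% of raw runs and 100% of log runs.

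**The case against.** Several parts of the opposing case stand.

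- A reader might infer that raw-scale results cannot be compared with the percentage benchmark. That is too strong: the point percentage follows from Table 14.2.7.3, and only its interval is missing.
- A reader might infer that the SAP breaks a promise to transform. It does not. Transformation in protocol 9.5.2.4 is conditional, and the sentence sits under secondary endpoints, while the biomarkers are exploratory. What remains is that its wording covers all outcomes analysed with a linear model, and the SAP gives neither the check nor a decision rule.
- The 20-40% figure is background on other drugs. It is an association, not a target for this study. It shows the scale on which the protocol discusses the marker, not a required analysis.
- The unstructured covariance lets variance differ between visits. That is right, but it does not stop high-baseline patients from dominating the raw mean change within a visit.
- The precision ratio is a power-type measure, and protocol 9.2.1 says the study is not powered for confirmatory analyses. The simulation is also a paired comparison rather than the planned mixed model. Both are fair limits on the size claimed.
- A reader might infer that BML volume has the same problem. The documents do not show this: they give no percentage effect for it, and no calculation with zero volumes was made. Medians, minima and maxima are already planned.

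**Conclusion.** The point holds in a limited form. The biomarkers are modelled untransformed and reported as absolute differences, the percentage the protocol discusses gets no interval, and the protocol's distribution and residual check is absent from the SAP. A log-scale model is a standard and better-matched choice for CTX-I and CTX-II.

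The size is illustrative: 1.2 to 2.4 times in squared t, resting on a multiplicative response, between-patient CV of 50-80%, within-patient CV of 30%, and reductions of 20-40%. None of the CVs comes from the documents. The gain for the percentage estimate itself is smaller, as the SDs above show. No confirmatory conclusion is at stake, so this is a desirable improvement and not a necessary correction.

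For BML volume, only the omitted check is established. It applies directly, since BML volume is a secondary endpoint in Population A.

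**What to change.** **Biomarkers.** Fit the 8.3.8.1 model to log(CTX-I) and log(urinary CTX-II/creatinine); the ratio is already in Listing 16.2.6.23. In Table 14.2.7.3, report the back-transformed geometric-mean percentage change with its CI, from each group's own biomarker baseline. Settle one confidence level, because the 8.1.1 code asks for 90% and the shells show 95%. Keep the raw summaries of Table 14.2.7.1.

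**Checks.** Restate in SAP 8.1.1 the distribution and residual check of protocol 9.5.2.4, and say what will be done if it fails.

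**BML volume.** Keep the planned model, apply the residual check, and add a signed-rank test with a Hodges-Lehmann estimate of within-group change as a supplement. Do not use log(volume+1). Volume is in mm³, so a move from 0 to 100 is ln 101 = 4.6 log units while 1000 to 2000 is ln(2001/1001) = 0.7. Switches between zero and non-zero would dominate, and the result would depend on an arbitrary constant.

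**Cost.** A small code change, re-labelled columns in Table 14.2.7.3 and its figure, and one extra BML estimate. TIC and Z-scores would stay on the raw scale, so each biomarker would appear on two scales, and a footnote should say so.
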